Hypothesis B: Activating the campaign will significantly increase the number of FEP referrals and patients admitted to OTNY as compared to number of FEP referrals and patients admitted pre-campaign. All OTNY referral data are thoroughly recorded as part of treatment as usual and stored in a centralized database within OTNY central. Extracted information includes the name and contact details of the individual making the inquiry, reason for the inquiry, presenting symptoms, duration of symptoms, age of the prospective patient, and outcome of the referral including OTNY intake/acceptance or screen out. For the duration of the award, all de-identified referral data routinely uploaded to OTNY central will be provided to research staff for analyses. We will extract OTNY referral data from each site prior to activing the campaign to serve as baseline, and will continue to extract all OTNY inquiry data during the active campaign. Additional referrals arriving through dedicated campaign channels (email, phone calls, text, live chat, and two way video) will be recorded centrally by research staff. All FEP referrals will be provided an appointment for an evaluation at the nearest OTNY program and admission to the program will be recorded. All ineligible referrals will be referred to appropriate local services. Based on existing OTNY inquiry data as well as the results of our prior pilot initiatives, we anticipate approximately doubling weekly inquiries as a result of the campaign, arriving through campaign related channels over the course of the trial (30 additional referrals). Of those, we anticipate that 20% will be appropriate for OTNY (6 participants weekly) and that 4 of those individuals will be successfully enrolled each week as a result of the campaign. We will compare baseline rates of inquiries, number of FEP referrals, and number of patients admitted to OTNY in NYS prior to campaign activation, to rate of inquiries, number of FEP referrals, and number of patients admitted to OTNY in NYS while the campaign is active both arriving through the campaign, and traditional referral channels.

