each will target a dedicated audience based on demographics (age) and online search query. For example, "I am hearing voices" will generate the participant ad/campaign, while "my daughter is acting strange" will generate an entirely different set of ads geared towards caregivers. Power Analysis: Current OTNY referral data suggest that caregivers including parents are 5 times more likely to initiate a referral inquiry as compared to prospective participants themselves. We therefore anticipate that at least 2/3 (66.7%) of campaign referrals (approximately 20 weekly) will be generated by the parent campaign. Based on OTNY referral data, we anticipate that 20% will be appropriate and all will be enrolled into OTNY. Sample size necessary to detect a prevalence of 66.7% for the caregiver campaign compared to the null hypothesis of equal rates for the two campaigns is 68, which has to be multiplied by the design effect (variance inflation factor), [1 + (n-1)p], to get required sample size. As ICC (p) ranges from 0.01 to 0.06, the design effect will range from 1.67 to 5.02 and the sample size required will vary from 114 to 342. Although there are 24 six-month time periods from all clusters (4 per cluster and 6 clusters, $4 \times 6 = 24$) based on the stepped wedge design for Aim 1, only 12 of them will have the campaign. Based on recent OTNY referral data, the number of enrolled subjects per cluster in a 6-month period varied from 26 to 34, with an average of approximately 30. Thus, we expect to have (30 x 12) 360 subjects enrolled from the campaign part of the stepped wedge design. This sample size will be sufficient to detect the hypothesized difference in rates (66.7% vs. 33.3%) at 80% power and α = 0.05, with an ICC as high as 0.06.

Aim 3: Explore which methods of online engagement are most effective at promoting treatment initiation by comparing rates of OTNY enrollment of individuals interacting with research staff via live chat or two-way video to rates of enrollment of individuals utilizing text, email, and/or phone alone. Hypothesis: individuals with FEP who engage via two-way video or live chat will be significantly more likely to initiate in-person contact compared to individuals with FEP who engage via text, email, and/or phone alone.

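### Aim 2's test of the caregiver share against 50% measures relative volume, not whether engaging caregivers makes treatment initiation more likely

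*Combined protocol and SAP*

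**What the plan says.** Section 12 (Aim 2) states the hypothesis as one about likelihood: reaching caregivers online should make it more likely that a person with first-episode psychosis starts treatment than reaching prospective patients does. It says that inquiries, FEP referrals and OTNY admissions will be compared between the two campaigns. The general analysis paragraph of Section 12 names z-tests for proportions with variance inflation, but does not say which proportion is tested.

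Only the Aim 2 power paragraph fixes that. It starts from current OTNY referral data, in which "caregivers including parents are 5 times more likely to initiate a referral inquiry as compared to prospective participants themselves". It continues: "We therefore anticipate that at least 2/3 (66.7%) of campaign referrals (approximately 20 weekly) will be generated by the parent campaign". It assumes that 20% of referrals will be appropriate and that all of these will enrol. The sample size is the number needed "to detect a prevalence of 66.7% for the caregiver campaign compared to the null hypothesis of equal rates for the two campaigns", given as 68. After inflation, "the design effect will range from 1.67 to 5.02 and the sample size required will vary from 114 to 342". For the number available, "we expect to have (30 x 12) 360 subjects enrolled from the campaign part of the stepped wedge design", which the plan calls enough for "the hypothesized difference in rates (66.7% vs. 33.3%) at 80% power and α = 0.05, with an ICC as high as 0.06".

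**The concern.** The powered quantity is the caregiver campaign's share of one total, with 50% as the no-effect value. A share of enrolments is driven by three things: how many people each campaign reaches, how many of those inquire, and how many inquirers enrol. The hypothesis concerns what engagement does to the chance of starting treatment. A share above 50% can arise from reach and inquiry volume alone.

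The plan itself expects this. It forecasts a majority of caregiver referrals because caregivers already make most of the inquiries, and it gives no reason to expect a different enrolment rate per referral. Nor does it equalise the two campaigns' audience size or ad reach. Aim 2 is, besides Aim 1, the only aim with a planned hypothesis test. A significant result could be reported as evidence that engaging caregivers works better when the data show only that more caregivers came through.

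**Working it through.** **Inputs, all from the Aim 2 power paragraph of Section 12:** null share 0.50; alternative 0.667; power 80%; α = 0.05 (two-sided assumed, since it reproduces the stated figure); ICC 0.01 to 0.06; 360 subjects; caregiver-to-self inquiry ratio 5:1; 20% of referrals appropriate and all enrolled.

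**1. The plan's figures.** One-sample test of a proportion:

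n = [1.96·√(0.5·0.5) + 0.842·√(0.667·0.333)]² / (0.667 − 0.5)² = 67.95, so 68.

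Design effect with n = 68: 1 + 67·0.01 = 1.67 and 1 + 67·0.06 = 5.02. Then 68·1.67 = 113.6 and 68·5.02 = 341.4, so 114 and 342. All stated figures reproduce.

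A two-sample comparison of 66.7% with 33.3% needs 34 per group, also 68 in total. But those two percentages cannot be enrolment rates per campaign: the plan's rate is 20%, and it derives 66.7% as a fraction of all campaign referrals. They are complementary shares of one total.

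**2. What the plan's figures imply for likelihood.** With 30 campaign referrals weekly, about 20 come through the caregiver campaign and 10 through the patient campaign. At 20%, enrolments are 20·0.2 = 4 and 10·0.2 = 2. The caregiver share is 4/6 = 66.7%; enrolment per referral is 20% in both. Section 12 (Hypothesis B) says 4 of 6 eligible people enrol, not all, but a common rate cancels and leaves the share at 66.7%.

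**3. What the test would declare.** Effective n is 360/5.02 = 71.7 (ICC 0.06) or 360/1.67 = 215.6 (ICC 0.01).

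| | ICC 0.01 | ICC 0.06 |
|---|---|---|
| Standard error under 50%, √(0.25/effective n) | 0.0341 | 0.0590 |
| Smallest significant share, 0.5 + 1.96·SE | 56.7% | 61.6% |
| z for an observed 66.7% | 4.89 | 2.82 |

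So the share forecast under equal enrolment likelihood is declared a caregiver advantage. If campaign enrolments simply followed the existing inquiry ratio, 5/(5+1) = 83.3%, the test would reject 50% with power above 99.9%.

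**4. How far the two quantities can diverge.** Let k be the patient campaign's enrolment rate per referral divided by the caregiver campaign's. With referrals split 2:1, the caregiver share is 2/(2 + k). It stays above 61.6% until k = 2/0.616 − 2 = 1.25, and above 56.7% until k = 2/0.567 − 2 = 1.53. Prospective patients could therefore be about 1.2 times (ICC 0.06) or 1.5 times (ICC 0.01) as likely to enrol per referral, and the test would still favour caregivers.

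**The case against.** The strongest reply is that Aim 2 is a head-to-head between two campaigns. Equal yield is a coherent null for that, and a service planner may well want to know which campaign brings in more patients. This stands: 50% is a legitimate null for relative volume. It does not turn a volume result into the likelihood result that the hypothesis states.

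It can also be said that the power paragraph is not the analysis specification, and that the test might turn out to compare rates per inquiry. That is possible, but then the stated sample size belongs to a different test, and no denominator per campaign is defined.

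Reach is partly observable. Sections 11 and 14 have ad and website engagement tracked by Google analytics and sent weekly, and the campaigns run simultaneously. But these data are not tied to the Aim 2 test, and spend is not mentioned.

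A reader might go further and infer that 50% is already known to be false, that the right null is the existing 83.3%, and that an observed 66.7% would mean a fall in the caregiver share. The documents do not support this:

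- The 5:1 ratio describes inquiries made to OTNY without the campaign. The caregiver share of enrolments and the share from other referrers are not given.
- Section 3 reports that youth with first-episode psychosis tend to search online before talking to others, so the mix of people answering search ads may differ.
- The 66.7% is a floor (at least two thirds) used as the powered alternative, not a point forecast.
- Whether the campaign changed the referral mix relative to traditional channels is a different question, which Aim 2 does not ask.

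**Conclusion.** The point holds as a mismatch between test and hypothesis. As sized, Aim 2 can establish that the caregiver campaign produced more enrolments than the patient campaign, and no more. On the plan's own figures, with equal enrolment per referral, the test is powered at 80% or more to declare for caregivers, and any share from about 57% (ICC 0.01) or 62% (ICC 0.06) of 360 suffices.

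This rests on reading the tested proportion from the power paragraph, on a two-sided 5% test, and on the plan's own design effects and count of 360. It is not sensitive to the count. If campaign enrolment runs at 4 weekly, spread evenly over six clusters, then 4·26/6·12 = 208 subjects are available; the thresholds become 58.8% and 65.2%, and 66.7% is still significant at ICC 0.06 (z = 2.15).

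The documents do not show that caregivers have no advantage. They show that this test cannot tell.

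**What to change.** - **Primary Aim 2 test.** Compare enrolment per inquiry between the caregiver and patient campaigns, with the cluster adjustment. Landing-page visitors or clicks could serve as the denominator instead. Section 12 already gives each campaign its own phone, email, text and chat lines, and campaign inquiries are recorded centrally. Because users may return repeatedly, define whether people or contacts are counted, and how a case is assigned if both a caregiver and the patient make contact.
- **Sample size.** Restate it for that contrast, with a stated difference in enrolment rates and a design effect suited to two campaigns running in the same clusters.
- **Share against 50%.** Keep it as a description of relative volume, reported with impressions, clicks and spend per campaign and beside the existing OTNY caregiver-to-self ratio. Spend is not among the listed data and would have to be added. For the OTNY ratio, Section 12 (Hypothesis B) says "Extracted information includes the name and contact details of the individual making the inquiry"; relationship to the patient is not listed, though the 5:1 figure implies that OTNY can classify it.
- **Conclusion wording.** If only the share is tested, limit the Aim 2 conclusion to which campaign brought in more enrolments.

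The cost is analysis-plan wording and a new calculation, using mostly data already collected. The downside is that the per-inquiry comparison may have less than the stated 80% power and may not favour caregivers; on the plan's single 20% figure the expected difference is zero. The two audiences also remain self-selected by search query and age, so the comparison describes the campaigns as run.

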12. STATISTICAL ANALYSIS

- Describe how your data will be used to test the hypotheses.
- State clearly what variables will be tested and what statistical tests will be used.
- *Include sample size calculations.*
- If this is a pilot study, state which variables will be examined for hypothesis generation in later studies.

A stepped-wedge cluster randomization (CR) design will be implemented. After a baseline period of six months, two clusters (grouped clinics) will be randomly assigned in month 7 and by month 18, all of NYS will be running the campaign. This strategy allows each region to serve as its own control³⁷. The treatment effect can be modeled as a random effect at the cluster level which will accommodate treatment heterogeneity across the clinics. We grouped the 21 OTNY sites into 6 clusters based on geolocation as well as the total number of FEP referrals at each clinic between 10/01/2017 to 09/30/2018. We combined some regions to ensure that each cluster will be able to successfully meet recruitment criteria. The six clusters are; 1) Bronx, 2) Manhattan, 3) Queens, 4) Brooklyn, 5) Hudson River/Central NY, 6) Staten

Version Date: 6.9.22 Page 12 of 31

Island/Long-Island/Western NY. There will be a total of four 6-month time periods, including the baseline period where all 6 clusters receive the control treatment. All analyses for Aim 1 (hypotheses A and B) will be conducted within the Generalized Linear Mixed Models (GLMM) framework with an identity link for continuous outcomes and logit link for binary outcomes. Analyses for Aim 2 will be done using asymptotic z-tests for proportions after accounting for the variance inflation factors (VIF). Aim 3 is exploratory, and hence only 95% confidence intervals, accounting for VIFs, will be calculated for the rates.

Aim 1: Evaluate the effectiveness of a search engine ad campaign on reducing DUP and raising rates of FEP referrals by directly comparing DUP and FEP referrals pre and post campaign activation. Hypothesis A: Patients admitted to OTNY via campaign channels will demonstrate a significantly shorter DUP than those admitted to OTNY through traditional outreach prior to campaign activation.

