Aim 2: Determine the efficacy of a campaign targeting caregivers in promoting treatment initiation by comparing rates of OTNY enrollment arriving through the caregiver campaign to rates of enrollment arriving through the patient campaign. Hypothesis: Engaging caregivers online will significantly increase the likelihood of promoting treatment initiation of individuals with FEP as compared to engaging prospective patients alone.

Throughout the campaign, one dedicated landing page for each unique target audience (prospective patients and caregivers), will be promoted online, presenting each audience with a unique and identifiable campaign phone line, email, text line, and live chat options. We will compare rates of inquiries, number of FEP referrals, and number of patients admitted to OTNY throughout NYS arriving through the caregiver campaign to rates of inquiries, number of FEP referrals, and number of patients admitted to OTNY arriving through the participant campaign. Both campaigns will run in parallel and

Version Date: 6.9.22 Page 14 of 31

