The campaign will encourage all website visitors to interact with research staff via phone, email, text, live chat, or two way video. During these interactions, research staff will obtain information regarding the eligibility of each user and facilitate treatment initiation if indicated as would be done for any other traditional OTNY referral. Research staff will record as much data as the user is willing to provide at the time. This includes the name and contact details of the individual, presenting concerns, presenting symptoms, duration of symptoms, age of the prospective patient, and outcome of the discussion including OTNY intake or screen out. As early help seeking is likely an ongoing process for many, users will be offered the opportunity to repeatedly return to our landing page as many times as they wish for ongoing online support. Each interaction will be recorded. Individuals with FEP will be referred to a local OTNY program for assessment. Based on rates of live chat

Version Date: 6.9.22 Page 15 of 31

utilization in prior marketing initiatives³², we anticipate that at least 30% of campaign website visitors will engage live chat/two way video at least once. Based on OTNY referral data, we anticipate that 20% will be eligible for OTNY. We will compare the rates of treatment initiation of individuals with FEP who engage in online two-way video or live chat support to rates of treatment initiation of individuals with FEP who interact with the campaign through phone, email, or text alone. Analysis for Aim 3 will be exploratory in nature, and hence a power analysis was not done.

In order to analyze qualitative interviews conducted throughout the trial, the study team would like to send the interview data to a Northwell approved transcription service (Perry Johnson & Associates). We will try to obtain verbal consent from all participants prior to sharing their data. If any participant refuses to provide consent, their data will not be sent for transcription.

Version Date: 6.9.22 Page 16 of 31

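### The exploratory Aim 3 comparison of contact modes pools the caregiver and patient campaigns, so it may be confounded by audience; a campaign-adjusted estimate is nearly free.

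*Combined protocol and SAP*

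**What the plan says.** All references are to the combined protocol and SAP.

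- **Contrast.** Section 12, Aim 3: "We will compare the rates of treatment initiation of individuals with FEP who engage in online two-way video or live chat support", set against "individuals with FEP who interact with the campaign through phone, email, or text alone". Neither group is divided by campaign.
- **Method.** Section 12, design paragraph: "Aim 3 is exploratory, and hence only 95% confidence intervals, accounting for VIFs, will be calculated for the rates". No covariate or stratification is named for Aim 3 anywhere.
- **Status.** Section 12, Aim 3: "Analysis for Aim 3 will be exploratory in nature, and hence a power analysis was not done". The Aim 3 hypothesis in Sections 4 and 12 nevertheless predicts a significant difference.
- **Audience as a driver of the outcome.** Section 12, Aim 2: "Engaging caregivers online will significantly increase the likelihood of promoting treatment initiation of individuals with FEP", compared with engaging patients. Section 4 has the same hypothesis.
- **Audience mix.** Section 12, Aim 2 power analysis: "at least 2/3 (66.7%) of campaign referrals (approximately 20 weekly) will be generated by the parent campaign".
- **Mode use.** Section 12, Aim 3: "we anticipate that at least 30% of campaign website visitors will engage live chat/two way video at least once". This is not broken down by campaign.
- **Identifiability.** Section 12, Aim 2 describes the landing pages as "presenting each audience with a unique and identifiable campaign phone line, email, text line, and live chat options".
- **Assignment.** Section 11 lets users choose how to make contact. It selects the ad and landing page from the search terms and the searcher's age.

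**The concern.** A crude comparison of two self-selected groups takes on the effect of any factor that both differs between the groups and affects the outcome. Aim 2 proposes audience as a factor that affects treatment initiation. Aim 3 then ignores it, although the two audiences see different ads and pages and each user chooses the mode. Accounting for a variance inflation factor widens the interval; it does not remove bias.

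If caregivers and patients favour different modes, a difference between chat/video and the other modes could partly reflect who made contact, or a real difference could be masked. Section 2 says the study aims to identify the tools most effective at encouraging treatment initiation, so readers will use this result even though it is labelled exploratory.

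**Working it through.** **1. The plan's own Aim 2 figure, to see what 66.7% means.** Aim 3 has no sample size, so the nearest stated figure is the 68 in the Aim 2 power analysis. A one-sample test of 0.667 against 0.5, two-sided α = 0.05, power 80%:

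n = [1.96 × 0.5 + 0.8416 × √(0.667 × 0.333)]² / 0.167² = 67.95, so 68. This reproduces.

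Design effect 1 + 67 × ICC: 1.67 at ICC 0.01 and 5.02 at 0.06. Then 68 × 1.67 = 113.56 → 114 and 68 × 5.02 = 341.36 → 342. Both reproduce.

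So 66.7% is the caregiver campaign's share, tested against an equal split. It is not an enrollment rate. The power analysis gives one conversion figure, 20%, and no separate one for the patient campaign. At 20% in both, 20 caregiver and 10 patient referrals a week give 4 and 2 enrolled: a share of 4/6 = 66.7% with identical conversion.

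**2. Size of the possible bias.** With no true mode effect:

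spurious difference = (caregiver share among chat/video users − caregiver share among others) × (caregiver initiation rate − patient initiation rate).

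The documents give neither factor by audience, so both are assumptions here.

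- Equal conversion in both audiences: 0, whatever the mode mix.
- Equal mode mix in both audiences: 0, whatever the conversion.
- Audience effect 10 points, share difference 20 points: 0.10 × 0.20 = 2 points.
- Audience effect 30 points, share difference 40 points: 0.30 × 0.40 = 12 points.

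A check held to the plan's totals uses a caregiver share of 2/3, 30% using chat/video, and 4 of 6 initiating. Assume rates of 75% (caregiver) and 50% (patient), which average (2/3)(0.75) + (1/3)(0.50) = 66.7%.

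- Caregivers 40% of chat users, so (0.667 − 0.3 × 0.40)/0.7 = 78.1% of others: (0.400 − 0.781) × 0.25 = −9.5 points.
- Caregivers 90% of chat users, so 56.7% of others: (0.900 − 0.567) × 0.25 = +8.3 points.

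The sign depends on which audience favours chat, and the plan does not say.

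**3. Precision of the pooled contrast.** Active time is 12 of 24 cluster-periods, half of 104 weeks, so 52 statewide-equivalent weeks. FEP cases: 30 × 20% = 6 a week, and 6 × 52 = 312. Applying the 30% visitor figure to FEP cases (an assumption) gives 94 v 218. With initiation at 4/6:

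SE = √[0.667 × 0.333 × (1/94 + 1/218)] = 5.8 points before inflation.

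Borrowing the Aim 2 design effects for illustration: 5.8 × √1.67 = 7.5 and 5.8 × √5.02 = 13.0 points. A bias of 2 to 12 points is then about 0.2 (2/13.0) to 1.6 (12/7.5) standard errors.

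**4. Precision after stratifying, before inflation.**

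- Patient campaign: 312/3 = 104 cases, 31 v 73; SE = √[0.222 × (1/31 + 1/73)] = 10.1 points.
- Caregiver campaign: 208 cases, 62 v 146; SE = √[0.222 × (1/62 + 1/146)] = 7.1 points.
- Mantel-Haenszel pooled: with equal mode mix the weights sum to 94 × 218/312 = 65.7, the same as the crude contrast, so the SE stays at 5.8. With the 40%/78.1% split they are 37.6 × 170.2/207.8 = 30.8 and 56.4 × 47.8/104.2 = 25.9, total 56.7; SE = √(0.222/56.7) = 6.3 points.

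**The case against.** The strongest reply is that the documents do not establish confounding. That stands. No section says that mode choice differs by audience, both audiences are offered the same contact options, and a difference in conversion is a hypothesis rather than a planning figure.

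Two stronger readings are tempting and are not supported:

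- A reader might take the power statement's 66.7% v 33.3% as two enrollment rates and conclude that the plan assumes the audiences convert differently. The calculation shows they are shares, with one conversion figure. That passage also has all appropriate referrals enrolling, whereas Section 8 and Hypothesis B have 4 of 6. If all enrolled, there would be no audience difference among eligible cases.
- A reader might infer from the Aim 3 wording about individuals with FEP who engage that caregiver contacts, two-thirds of the data, fall out of scope. Aim 2 counts patients admitted through the caregiver campaign, so the natural unit is the FEP case, whoever made contact. The wording deserves tightening, but exclusion is not its natural sense.

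It is also fair to say that Aim 3 is exploratory, without a power analysis, and that no primary result depends on it. This limits the consequence. It does not justify leaving in an avoidable source of bias that the plan itself points to and can already identify.

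Finally, stratifying is only a partial remedy. The landing page depends on keywords and age, so it is a proxy for who made contact. Motivation and severity may still drive mode choice within each audience. Both limits stand.

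**Conclusion.** The point holds in a limited form. Aim 3 as written is a crude contrast of self-chosen modes over two pooled audiences, and Aim 2 hypothesises that audience affects the same outcome. The contrast may be confounded; the documents do not show that it is. The direction is unknown. The size runs from zero to roughly 12 points under the assumed ranges, and a wider assumed audience gap would enlarge it. Against an inflated standard error of about 7.5 to 13 points, the bias could be negligible or could exceed one standard error.

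These figures rest on assumed audience and mode differences, on applying the 30% visitor figure to FEP cases, on 4 of 6 initiating, and on borrowing the Aim 2 design effects. No stated sample size changes and Aim 1 is untouched. The change is worth making because it costs little, not because Aim 3 is shown to be wrong.

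**What to change.** In the Aim 3 part of Section 12:

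1. Make the main estimate a campaign-adjusted difference in treatment initiation, chat/video minus phone/email/text alone: Mantel-Haenszel, stratified by caregiver v patient campaign of origin, with the 95% confidence interval accounting for the VIF.
2. Show the two campaign-specific differences descriptively.
3. Define the population as FEP cases for whom the patient or a caregiver made contact. Since repeat visits are allowed, state which campaign counts when a case has used both.
4. State that campaign of origin is a proxy for who made contact, that self-selection into mode by motivation or severity remains, and that the result is exploratory and associational.

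**Cost.** SAP wording only; the separate channels should supply the stratum without new data collection. The adjusted pooled interval changes little (SE before inflation 5.8 to about 6.3 points in the example above). The campaign-specific intervals are clearly wider: SE before inflation about 10 points for the patient campaign and 7 for the caregiver campaign. That is why they should be descriptive. Adding the six clusters as further strata would give 12 strata with about 31/6 ≈ 5 chat/video cases per patient-campaign cluster, so clustering is better left to the VIF.
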